### ***Sample size for Pilot Trial***

For the full-scale trial, a minimum of 43 participants must be recruited annually per site on average. The LHSC Victoria Campus ED treats approximately 130 patients with DKA annually, based on our hospital's Decision Support data from the most recent fiscal year (Mar 1 2019 – Feb 29 2020).

DKA by Site	Patients
Victoria Hospital	130
(E1010) Type 1 DM with ketoacidosis	70
(E1110) Type 2 DM with ketoacidosis	51
(E1112) Type 2 DM with keto & lactic acidosis	1
(E1410) Unspecified DM with ketoacidosis	8

Based on our research team hours of coverage (0700-2300) and past data from ED presentation time of potentially eligible patients, we expect to approach at least 104 (80%) of eligible patients in the one-year pilot study period, and a minimum of 43 approached participants (41.3%) must be recruited to meet the feasibility target. According to data from similar past trials, we

anticipate being able to recruit at least 50% of approached patients (target sample size of 52 patients, 26 in each arm). With 104 patients approached per year, a 90% two-sided confidence interval around the anticipated recruitment rate will have a total width of 0.17, i.e. a lower limit of 0.415 and an upper limit of 0.585. Because the lower limit excludes the minimum feasibility target of 41.3%, we can be 90% confident that the future trial is feasible.

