### ***Study Population – Inclusion/Exclusion Criteria***

There are no definitive criteria for diagnosing DKA. Thus, using the criteria employed by Self et al. and the Diabetes Canada guidelines we will include ED patients  $\geq 18$  years with a clinical diagnosis and laboratory values consistent with DKA, including:

- plasma glucose concentration  $\geq 14$  mmol/L
- plasma bicarbonate concentration  $\leq 18$  mmol/L and/or blood pH  $\leq 7.30$
- calculated anion gap  $> 10$  mmol/L
- presence of ketones/beta-hydroxybutyrate in serum and/or urine

We will exclude patients who:

- Are initially seen at another ED and transferred to LHSC for care and/or admission
- Receive  $> 1$  L of IV fluid prior to enrolment (e.g. pre-hospital by EMS or while waiting to be seen) – this may cause study contamination
- Are initially enrolled due to clinical suspicion of DKA based on elevated point-of-care glucose, but ultimately do not meet clinical/laboratory criteria for DKA (e.g. “hyperglycemia” only)
- Have euglycemic DKA (generally those on SGLT-2 inhibitors)

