We plan to conduct the full-scale trial at 6 ED sites over 2 years, which would require an average minimum recruitment of 86 participants per site (43 per site per year). Our research group has established relationships with these other Canadian EDs where we have previously conducted successful studies. If further sites are needed for recruitment, we will leverage the Network of Canadian Emergency Researchers (NCER).

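### The pilot's recruitment forecast counts all 130 coded DKA patients as eligible, and its 90% confidence statement fails if even one to three of them are not

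*Combined protocol and SAP*

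**What the plan says.** The section Sample size for Pilot Trial starts from hospital data for one fiscal year: "The LHSC Victoria Campus ED treats approximately 130 patients with DKA annually". The table beneath it splits these patients by diagnosis code (70 + 51 + 1 + 8 = 130). The number to be approached is then derived with this stated basis: "Based on our research team hours of coverage (0700-2300) and past data from ED presentation time of potentially eligible patients". The result is that "we expect to approach at least 104 (80%) of eligible patients in the one-year pilot study period".

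The target follows: "a minimum of 43 approached participants (41.3%) must be recruited to meet the feasibility target". The 43 comes from the full-scale plan of 516 participants at 6 sites over 2 years. The section anticipates recruiting half of those approached, which gives 52. It adds that "a 90% two-sided confidence interval around the anticipated recruitment rate will have a total width of 0.17", running from 0.415 to 0.585. Because 0.415 lies above 41.3%, it concludes with 90% confidence that the future trial is feasible.

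The Inclusion/Exclusion Criteria remove several groups who would carry a DKA code. One is patients who "Are initially seen at another ED and transferred to LHSC for care and/or admission". Others are patients given more than 1 L of IV fluid before enrolment and patients with euglycemic DKA. The criteria also set a glucose threshold of 14 mmol/L.

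**The concern.** A count of diagnosis codes is not a count of eligible patients. The plan applies one reduction, for coverage, and calls the result a share of eligible patients. Its own exclusions are not deducted anywhere.

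This matters because the needed number, 43, does not shrink with the eligible pool. Each ineligible patient raises the recruitment rate that is required and also lowers the confidence limit compared with it. The figures affected (104, 52, 41.3% and the confidence statement) make up the plan's only numerical feasibility criterion, and recruitment rate is the primary feasibility outcome. The count and the percentage also agree only if 104 are approached. With 94 approached, for example, 41.3% is about 39 patients (0.413 × 94 = 38.8), short of 43.

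**Working it through.** **Inputs from the protocol.** 130 coded patients; 80% approached; 50% anticipated recruitment; 43 required per site per year (516 / 6 / 2 = 43); 90% two-sided interval of 0.415 to 0.585.

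**Input not in the protocol.** The number of the 130 who would be excluded. It is varied below as an assumption.

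**Step 1: where 104 comes from.** 104 / 130 = 0.800, so the whole coded count is the denominator.

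**Step 2: reproduce the plan's interval.** The exact (Clopper-Pearson) 90% interval for 52/104 is 0.4154 to 0.5846, width 0.169, which matches the stated figures. The lower limit is 0.4194 by Wald and 0.4204 by Wilson. The required rate is 43/104 = 0.4135. The criterion is met by all three methods at 104 approached. By the exact interval the margin is 0.4154 − 0.4135 = 0.0019.

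**Step 3: remove k ineligible patients.** Approached n = 0.8 × (130 − k); required rate = 43/n; lower limit taken at a 50% rate. Fractional n is kept so that rounding does not decide the answer.

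| k | n | Required | Exact | Wald | Wilson |
|---|---|---|---|---|---|
| 0 | 104.0 | 0.4135 | 0.4154 pass | 0.4194 pass | 0.4204 pass |
| 1 | 103.2 | 0.4167 | 0.4150 fail | 0.4190 pass | 0.4201 pass |
| 2 | 102.4 | 0.4199 | 0.4147 fail | 0.4187 fail | 0.4198 fail |
| 3 | 101.6 | 0.4232 | 0.4143 fail | 0.4184 fail | 0.4195 fail |

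The Wilson failure at k = 2 is by 0.0001, so k = 3 is the first clear failure by every method. Rounded to 102 approached with 51 recruited, the exact lower limit is 0.4145 against 43/102 = 0.4216.

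**Step 4: what this means for reaching 43.** If the true recruitment rate is 50%, the number recruited is binomial (n, 0.5). The shares below are assumptions; n is rounded.

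| Assumed ineligible | Approached | Expected recruits | Required rate | P(at least 43) |
|---|---|---|---|---|
| 0% | 104 | 52 | 0.413 | 0.969 |
| 2% | 102 | 51 | 0.422 | 0.954 |
| 10% | 94 | 47 | 0.457 | 0.82 |
| 20% | 83 | 41.5 | 0.518 | 0.41 |

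**Step 5: break-even.** Expected recruits equal 43 when the eligible fraction is 43 / (130 × 0.8 × 0.5) = 43/52 = 0.827. Expected enrolment therefore falls below 43 once more than about 17.3% are ineligible.

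**The case against.** The plan's arithmetic is correct throughout; what is at fault is an unstated assumption about the eligible pool. That stands.

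The fragility is not peculiar to exclusions. With all 104 approached, one fewer consent (51/104) gives an exact lower limit of 0.406, already below 0.4135, while one more (53/104) gives 0.425. The root cause is a margin of 0.002 on hypothetical data from an approximate count. This also stands, and it is a further reason not to rest a confidence statement on that margin. It does not excuse labelling every coded patient as eligible.

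There may be offsets. The plan says at least 104 and at least 50%, and the Screening, Consent, and Enrolment section lets treating physicians enrol after hours. These could make up some of the loss. None is quantified, and the plan's own calculation uses exactly 104 and 50%.

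The documents do not say whether the hospital count already omits transfers, or how many patients were euglycemic or had received more than 1 L. The size of the shortfall is therefore unknown.

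A reader might infer that the pilot is set to be judged on percentage alone and could pass with fewer than 43. The documents do not support that in full. The target is stated first as a count of 43 with the percentage in parentheses, although a later sentence calls 41.3% the minimum target, which leaves some ambiguity.

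**Conclusion.** The point holds. The forecast takes 80% of all coded DKA patients without allowing for the stated exclusions, and the confidence statement cannot survive even a trivial allowance: 1 ineligible patient of 130 with the interval that reproduces the plan, 2 with Wald or Wilson.

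A reader might go further and infer that the full trial is not feasible. The documents do not support this. If the true recruitment rate is 50%, losing 2% of the pool moves the chance of reaching 43 only from 0.969 to 0.954. The serious figures (0.82 at 10% ineligible, 0.41 at 20%) depend on assumed shares. The 43 is also an average across sites, the full-scale plan allows for further sites, and the pilot will measure recruitment directly. What falls is the stated confidence, along with the standing of 104, 52 and 41.3% as figures for eligible patients.

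**What to change.** In Sample size for Pilot Trial:

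1. Apply the exclusion criteria to the same fiscal year's records before taking 80%. If that is not possible, show results over an assumed range of 0 to 30% ineligible.
2. Restate the expected number approached, the expected enrolment and the required rate.
3. Make the count already in the text govern: at least 43 eligible, confirmed-DKA patients enrolled in 12 months. Show 41.3% only as its equivalent at 104 approached. Specifying confirmed DKA matters because the plan enrols possible cases and later removes those who do not meet the criteria.
4. Delete the 90% confidence sentence, or recompute it from the revised figures.

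The cost is a records query or a small table, and a stated target that looks somewhat less favourable. No extra patients are needed and trial conduct does not change.

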## **STUDY OBJECTIVE(S); INCLUDING SPECIFIC AIMS AND/OR HYPOTHESES**

We hypothesize that patients who are administered IV RL will have faster DKA resolution without a concomitant increase in adverse outcomes when compared with normal saline. However, a pilot randomized controlled trial (RCT) is necessary to assess the feasibility of a future multi-centre trial. Our specific objectives for this pilot study are to determine the feasibility of conducting a full-scale multi-centred RCT and to use this pilot data to inform the future trial.

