#### ***Sample size for Full-Scale Trial***

The sample size calculation for this trial was based on a study of Clinical Effects of Balanced Crystalloids vs Saline in Adults with Diabetic Ketoacidosis which compared the clinical effects of balanced crystalloids with the clinical effects of saline for the acute treatment in DKA in two clinical trials (Isotonic Solutions and Major Adverse Renal Events Trial [SMART] and the

Saline Against Lactated Ringer's or Plasma-Lyte in the Emergency Department [SALT-ED]10). The primary outcome for this comparison was the time between ED presentation and DKA resolution, measured in hours. Self et al. (2020) found an absolute reduction in time to DKA resolution of 3.9 hours. In the balanced crystalloids group (n=94), the median time to resolution of DKA was 13.0 hrs [IQR: 9.5-18.8], while in the saline group (n=78) the median time to resolution was 16.9 hrs [IQR: 11.9-34.5]. The IQR was used to calculate the standard deviation for each group based on the following assumption for normally distributed data:  $SD=IQR/1.35$ . The pooled standard deviation was then calculated based on the sample size and standard deviation of each group from the Self et al. (2020) study [ $\sqrt{((n1-1)*SD1^2 + (n2-1)*SD2^2)/(n1+n2-2)}$ ] and was determined to be 12.37. To establish superiority of balanced crystalloids versus saline in the time to resolution of DKA, a superiority margin for a clinically significant difference was chosen to be a 40% (=6.76 hours) reduction in time to resolution of DKA based on expert consensus and patient partner feedback. A conservative attrition rate of 10% was selected for the sample size calculation, as loss to follow-up rates should be low given the nature of the intervention (IV fluids) and follow-up period (<24 hours). The actual attrition rate determined by this pilot study will inform the sample size calculation for the full-scale multicentre study. Therefore, to achieve 80% power at the 5% level of significance with equal allocation, the sample size for the balanced crystalloids (Ringer's lactate) group and the saline group, while accounting for a 10% loss to follow up and a 25% reduction in time to DKA resolution, is 516 participants (258 per group). The sample size was calculated using Wang and Ji's (2020) method for common clinical study designs available at <http://riskcalc.org:3838/samplesize/>.

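### The 41.3% recruitment threshold uses only this hospital's DKA volume, so meeting it supports feasibility at this site; feasibility of the six-site trial does not follow without the other sites' volumes

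*Combined protocol and SAP*

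**What the plan says.** The stated objective is to "determine the feasibility of conducting a full-scale multi-centred RCT", and the primary feasibility outcome is the recruitment rate over one year at a single hospital.

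The section Sample size for Full-Scale Trial sets the requirement: the total "is 516 participants (258 per group"), to be enrolled at six emergency departments over two years, which means "an average minimum recruitment of 86 participants per site (43 per site per year"). It supports the choice of sites by the group's existing ties and past studies with the other departments, and it allows for more sites through a research network if recruitment calls for them.

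The section Sample size for Pilot Trial turns this into a local criterion. The hospital sees about 130 DKA patients a year and expects to approach 104 of them (80%), and "a minimum of 43 approached participants (41.3%) must be recruited to meet the feasibility target". It anticipates 50% (52 patients), gives a 90% interval of 0.415 to 0.585, notes that the lower limit exceeds 41.3%, and concludes with 90% confidence that the future trial is feasible.

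**The concern.** The numerator and denominator of 41.3% come from different places. The numerator, 43, is an average over six sites. The denominator, 104, belongs to one hospital. The percentage is therefore the recruitment rate at which this hospital supplies its own average share. It is the right threshold for six sites together only if the other five, taken as a group, have the same number of DKA patients per site and approach and recruit the same fractions of them.

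The documents give no DKA volume, coverage hours or approach fraction for those five sites. Past collaboration says nothing about how many DKA patients they see. At stake is the decision the pilot exists to inform: the rule can pass a six-site trial that will fall short of 516 in two years, or turn down one that would reach it.

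**Working it through.** **Inputs.** From Sample size for Full-Scale Trial: 516 participants, 6 sites, 2 years. From Sample size for Pilot Trial: 130 DKA patients a year, 104 (80%) approached, threshold 43, anticipated recruitment 50%, 90% interval 0.415 to 0.585. The mean annual volume V of the other five sites is not given; values of V below are assumptions.

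**1. Reproducing the plan's figures.**
- 516 / (6 × 2) = 43 per site per year.
- 0.80 × 130 = 104, and 43/104 = 0.4135.
- 0.50 × 104 = 52.
- 90% interval for 52/104: exact (Clopper-Pearson) 0.4154 to 0.5846; continuity-corrected normal 0.4145 to 0.5855. The stated interval agrees with these. The stated lower limit clears the threshold by about 0.2 of a percentage point.

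The 516 is taken as given here.

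**2. Volume the other five sites need.** Let r be the recruitment rate among those approached. With 80% approached everywhere, each DKA patient yields 0.8r recruits. Six sites need 516/2 = 258 a year, so

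V = (258 − 130 × 0.8r) / (5 × 0.8r).

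| r | Recruits per DKA patient | V needed |
|---|---|---|
| 43/104 (threshold) | 0.331 | 130 |
| 0.415 (stated lower limit) | 0.332 | 129 |
| 0.50 (anticipated) | 0.400 | 103 |
| 0.585 (stated upper limit) | 0.468 | 84 |

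For the second row: (258 − 43.16) / 1.66 = 129.4.

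**3. Threshold implied by other volumes.** Turning the formula round, the common recruitment rate needed is 258 / (0.8 × (130 + 5V)), and the two-year total is 2 × 0.8r × (130 + 5V).

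| Assumed V | Rate needed | Total at 43/104 | Total at 50% |
|---|---|---|---|
| 150 | 258/704 = 36.6% | 582 | 704 |
| 130 | 258/624 = 41.3% | 516 | 624 |
| 100 | 258/504 = 51.2% | 417 | 504 |
| 80 | 258/424 = 60.8% | 351 | 424 |

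A fixed 41.3% is too lenient if the other sites are smaller than this one and too strict if they are larger.

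**4. What adding sites would do.** With V = 100 assumed for every added site, 516 in two years takes 8 sites in total at the threshold rate and 7 at 50%.

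**The case against.** The strongest reply is that the plan does most of what a single-site pilot can. It estimates a recruitment proportion with an interval, and a proportion is what carries over to other hospitals. Partner volumes are a matter for site selection and cannot be measured in one department. The objectives also include informing the later trial, and the full-scale section already allows for more sites. At the anticipated 50% with V = 100, the shortfall is 516 − 504 = 12 patients, or under three weeks at 252 a year.

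Much of this stands, and it rules out three stronger readings that a reader might infer.

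- *That 43 is itself fitted to this hospital.* It is not; it is 516/6/2. Only its conversion to 41.3% is local.
- *That the six-site trial is infeasible unless the other sites average about 130.* That figure holds only at or near the threshold, and only if both fractions carry over. At 50%, 103 is enough, and better approach or consent elsewhere would offset lower volume. Equally, 130 is not sufficient on its own if those fractions are worse.
- *That the trial will fall short.* The documents give no partner volumes, so the shortfalls in the table are illustrations.

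What the reply does not answer is the inference drawn. The confidence statement rests on the lower limit of 0.415, not on 50%, and at 0.415 the other sites must average about 129. The provision for further sites is not tied to any pilot result, so nothing in the plan says when it would be used.

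**Conclusion.** The feasibility figures are arithmetically correct, but the six-site conclusion does not follow from them. Meeting 43 of 104 shows that this hospital can supply an average share. Extending that to six sites assumes, without saying so, that the others average about 130 DKA patients a year at the same approach and recruitment fractions. Over an assumed range of 80 to 150, the rate needed runs from 60.8% down to 36.6%, so the error could go either way and the documents cannot say which. These figures rest on the stated 80% approach fraction, a common recruitment rate across sites, and a target of 516. The weakness lies in the decision rule and the claim made from it. The choice of recruitment rate as the primary feasibility outcome is sound.

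**What to change.** 1. In Sample size for Pilot Trial, limit the confidence statement to feasibility at this site.
2. Ask each intended partner site (the documents do not name them) for its annual DKA count, using the same coded query as for this hospital.
3. For the six-site decision, define the pilot yield as confirmed, enrolled DKA patients divided by coded DKA patients at this site over the year. This absorbs eligibility, approach and consent in one ratio. A product of approach and consent fractions would not, because patients are approached as possible DKA and some are excluded later.
4. Proceed if the lower confidence limit of the yield, multiplied by the summed annual volume of the planned sites, is at least the required annual enrolment: 258 under the current 516, updated if the full-scale sample size is revised.
5. If it falls short, report the number of sites or years needed. That ties the pilot result to the existing provision for further sites.

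The cost is one administrative data request and a rewritten criterion; enrolment and treatment in the pilot are unchanged. The threshold may become less favourable. For example, 52 enrolled of 130 gives a yield of 0.40 with a lower 90% limit of 0.40 − 1.645 × √(0.40 × 0.60/130) = 0.329. Even if all six sites saw 130, this gives 0.329 × 780 = 257 a year, one short of 258. Transfer of the yield to other sites remains an assumption and should be stated as one.

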### ***Study Outcomes***

#### **Primary Feasibility Outcome**

The primary feasibility outcome is patient recruitment rate over the one-year study period. We will also measure adherence to the protocol for this pilot study. This pilot is not powered to determine differences in treatment groups; however, a priori outcome definition and accurate outcome assessment is needed to inform the future study.

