#### ***Sample Size***

The full-scale multi-centred will include 516 participants (258 per arm), assuming  $\alpha=0.05$ , power=80%, 1:1 allocation, a 40% (6.76 hours) minimal clinically important reduction in DKA resolution time, and 10% attrition rate. This trial will be conducted at 6 ED sites over 2 years. Based on this, the sample size for this local pilot RCT is 52 participants (26 per arm).

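### The 90% feasibility statement holds only if 104 patients are approached; once yearly volume may vary, 52 recruits in a year no longer clearly exclude the required 43

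*Combined protocol and SAP*

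**What the plan says.** Under Primary Feasibility Outcome: "The primary feasibility outcome is patient recruitment rate over the one-year study period". The requirement comes from the full-scale design. Six sites over two years "would require an average minimum recruitment of 86 participants per site (43 per site per year)", and Sample size for Pilot Trial repeats that "a minimum of 43 participants must be recruited annually per site on average".

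The same section then moves from a count to a proportion. It starts from one fiscal year of hospital data ("The LHSC Victoria Campus ED treats approximately 130 patients with DKA annually"), projects the number approached ("we expect to approach at least 104 (80%) of eligible patients in the one-year pilot study period"), and restates the target on that base: "a minimum of 43 approached participants (41.3%) must be recruited to meet the feasibility target". With recruitment of at least half of those approached, the target is 52, and Sample Size confirms that "the sample size for this local pilot RCT is 52 participants (26 per arm)".

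The precision statement is "With 104 patients approached per year, a 90% two-sided confidence interval around the anticipated recruitment rate will have a total width of 0.17", with limits 0.415 and 0.585. Because 0.415 exceeds 41.3%, the section ends by claiming 90% confidence that the future trial is feasible. The Data Analysis section gives no other analysis of recruitment.

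**The concern.** The requirement is a number of patients per unit time. The interval is for a proportion among a fixed number approached. The two match only if exactly 104 patients are approached, because 41.3% is 43 divided by 104. That 104 is a projection, 80% of one past year's 130 cases. The binomial interval carries the chance variation in who consents. It carries none of the variation in how many patients with DKA present and are approached.

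This conclusion is the only inferential statement that the plan makes about its primary outcome, and it supports the step to a 516-patient trial. If it depends on an unstated assumption about volume, the pilot could reach its target of 52 and be reported as having shown more than it did.

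**Working it through.** **Inputs.** Requirement: 516 / 6 sites / 2 years = 43 per site-year (Sample size for Full-Scale Trial). Annual cases 130, approached 0.80 × 130 = 104, recruited 0.50 × 104 = 52, two-sided 90% level (all from Sample size for Pilot Trial).

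**1. The plan's own figure.** The exact (Clopper-Pearson) 90% interval for 52/104 is 0.4154 to 0.5846, width 0.169. This reproduces the stated limits. The threshold is 43/104 = 0.4135. On the count scale the lower limit is 104 × 0.4154 = 43.2, against 43, so the margin is 0.2 patients.

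**2. The same method with slightly fewer approached, consent held at 50%.**

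| Approached | Exact lower limit | Needed (43/approached) | Clears? |
|---|---|---|---|
| 104 | 0.4154 | 0.4135 | yes |
| 103 | 0.4149 | 0.4175 | no |
| 102 | 0.4145 | 0.4216 | no |

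The row for 103 uses the notional 51.5 recruits. There the simple normal (Wald) interval would still pass (0.4190), but at 102 it fails too (0.4186 against 0.4216). If the number approached were Poisson with mean 104, its central 90% range would be about 88 to 121.

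**3. An interval for the yearly count.** Assumption: recruits in a year follow a Poisson distribution. The fixed-104 model gives the count a variance of 104 × 0.5 × 0.5 = 26; the Poisson model gives about 52.

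- Exact two-sided 90% interval for 52: lower χ²(0.05; 104)/2 = 40.7, upper χ²(0.95; 106)/2 = 65.5. It includes 43.
- Other Poisson forms: Wald 40.1 to 63.9, score 41.4 to 65.3, log 41.4 to 65.3, square root 40.8 to 64.5. All include 43.
- One-sided 90% exact lower limit: χ²(0.10; 104)/2 = 42.999.
- Chance of 52 or more if the true rate is 43 per year: 10.0% under Poisson, 4.6% under the fixed-104 model.

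**4. An intermediate model: 130 cases fixed, recruitment of 52/130.** 90% lower limits on the count scale are 42.6 (exact), 42.8 (Wald), 43.1 (Jeffreys) and 43.2 (Wilson). Whether 43 is excluded depends on the method.

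**5. What would clear 43 under the exact Poisson interval.** The lower limit is 42.5 at 54 recruits and 43.4 at 55, so 55 is needed in a full year. If enrolment stops at the 52nd recruit after T years, the lower limit for the rate is 40.73/T. This exceeds 43 when T < 40.73/43 = 0.947 years, or 11.37 months. Rounded down, that is about 11.3 months.

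**The case against.** The best defence is that the plan states its condition: the precision sentence opens with the number approached, and the binomial calculation is right on that condition. It is also a planning calculation, since no interval for the observed primary outcome is prespecified. Both points stand. But the closing sentence drops the condition and speaks of the feasibility of the future trial without qualification.

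Exceeding a minimum is a one-sided claim, and the one-sided 90% Poisson limit is 42.999 against 43. Read that way, a 90% statement is met to rounding. This stands and limits the size of the point: what is lost is the exclusion by the two-sided lower limit, a drop from about 95% to about 90% one-sided confidence.

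The Poisson model is not in the documents, which give a single year's volume and no variance. With 130 cases fixed the answer is borderline. This also stands, so Poisson should be presented as an assumption with a range. Overdispersed arrivals would widen the interval further.

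Recruitment rate might mean the proportion of those approached, as the pilot sample-size section uses the term, and the consent proportion may transfer better to other sites. The requirement is also an average over six sites, which one site's count does not describe either. These are reasons to report both quantities. They do not make 41.3% equivalent to 43 per year when the number approached differs from 104.

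A reader might infer that the plan's conclusion reverses, or that the trial is infeasible. The documents support neither. The figures of 104 and 50% are stated as minimums, 55 or more recruits would clear 43, and the full-scale section provides for adding sites if recruitment is short.

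**Conclusion.** The point holds in a limited form. The stated interval is correct for 104 approached, but its margin over the threshold is 0.2 patients and does not survive a shortfall of one or two approached patients at 50% consent. Allowing for variation in volume under a Poisson assumption, 52 recruits in a full year give 40.7 to 65.5 and do not exclude 43 at the two-sided 90% level. The unconditional feasibility statement is therefore not supported at the planned 52 by the criterion that the plan itself uses. The result rests on the Poisson assumption and on a count of exactly 52. It affects how the primary outcome is interpreted, not patient safety or any comparison between the arms.

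**What to change.** - In Primary Feasibility Outcome and Sample size for Pilot Trial, report recruits per site-year with an exact Poisson 90% interval compared with 43. Check monthly counts for overdispersion. Report the consent proportion alongside.
- Replace the last sentence of Sample size for Pilot Trial with text such as: The binomial interval is conditional on 104 patients being approached. Allowing for variation in patient volume (Poisson assumption), 52 recruits in a full year give a 90% interval of 40.7 to 65.5 per year, which does not exclude 43.
- State the pass rule in a form compatible with the sample size of 52: at least 55 recruited in 12 months or, if enrolment closes at 52, the 52nd recruit within about 11.3 months (gamma interval on elapsed time). The plan must say which applies, because 55 cannot be reached if enrolment stops at 52.

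The cost is wording, one further interval formula, and a decision on whether enrolment stops at 52 or runs the full year. Closing at 52 needs no extra patients; running the year to allow 55 would mean enrolling beyond the stated sample size. The downside is that the planning conclusion becomes less favourable than the one now printed.
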